## SCHEMA

If only three participants were enrolled at the RP2D level, then an additional 3 participants will be enrolled to confirm that  $\leq 1$  out of 6 participants experiences a DLT at this dose.

If two out of three (or two out of six) participants at 250 mg daily have a DLT, then this dose will be considered to be too toxic in this population.

---

CONFIDENTIAL

This document is confidential. Do not disclose or use except as authorized.

## 1. OBJECTIVES

### 1.1 Study Design

This is a prospective, non-randomized, open-label, multi-center, phase I study of the mutant *IDH1* inhibitor, ivosidenib, given to patients with *IDH1*-mutant myeloid neoplasms after hematopoietic stem cell transplantation (HSCT).

### 1.2 Primary Objectives

To identify the recommended phase 2 dose (RP2D) of ivosidenib in patients with *IDH1*-mutant myeloid neoplasms after hematopoietic stem cell transplantation.

To explore the safety and tolerability of ivosidenib in patients with *IDH1*-mutant myeloid neoplasms in the post-stem cell transplant setting.

### 1.3 Secondary Objectives

To detect and categorize, according to severity, ivosidenib-related toxicities in patients with *IDH1*-mutant myeloid neoplasms receiving ivosidenib after hematopoietic stem cell transplantation.

To examine the cumulative incidence of acute GVHD from start of ivosidenib in patients with *IDH1*-mutant myeloid neoplasms who receive ivosidenib after hematopoietic stem cell transplantation.

To examine the cumulative incidence of chronic GVHD from start of ivosidenib in patients with *IDH1*-mutant myeloid neoplasms who receive ivosidenib after hematopoietic stem cell transplantation.

To monitor plasma and marrow 2-hydroxyglutarate levels in patients with *IDH1*-mutant myeloid neoplasms who receive ivosidenib after hematopoietic stem cell transplantation.

To assess *IDH* clonal evolution and mutational burden in patients with *IDH1*-mutant myeloid neoplasms who receive ivosidenib after hematopoietic stem cell transplantation.

To measure minimal residual disease (MRD) in patients with *IDH1*-mutant myeloid neoplasms who receive ivosidenib after hematopoietic stem cell transplantation, through measurement of mutant IDH1 (mIDH1) allelic burden.

### 1.4 Exploratory Objectives

To examine the rate of relapse of *IDH1*-mutant myeloid neoplasms in patients receiving ivosidenib after hematopoietic stem cell transplantation.

To examine relapse-free survival in patients with *IDH1*-mutant myeloid neoplasms who receive ivosidenib after hematopoietic stem cell transplantation.

CONFIDENTIAL

This document is confidential. Do not disclose or use except as authorized.

To examine overall survival in patients with *IDH1*-mutant myeloid neoplasms who receive ivosidenib after hematopoietic stem cell transplantation.

## 2. BACKGROUND

### 2.1 Study Disease

Acute myeloid leukemia (AML) and myelodysplastic syndromes (MDS) are lethal hematologic malignancies associated with a poor prognosis. The estimated number of deaths from AML is nearly as many as the incidence of new diagnoses. While the majority of patients with AML achieve a complete remission with conventional cytotoxic induction therapy, approximately half subsequently relapse and most die from their disease (Dohner 2015, Tefferi 2009, Gangat 2016). Outcomes are far worse for those with relapsed or high-risk AML, such as those with adverse cytogenetics or with a history of preceding myelodysplastic or myeloproliferative conditions. Allogeneic hematopoietic stem cell transplantation (HSCT) is recommended as an appropriate consolidative approach for suitable patients with higher risk disease. The ongoing characterization of prognostically important chromosomal and molecular alterations in AML has engendered hope that novel and effective targeted therapies can be developed for this patient population.

### 2.2 IDH Inhibitors

Genomic sequencing of myeloid malignancies, including MDS and AML, has recently led to the discovery of a series of mutations, including those impacting the genes encoding isocitrate dehydrogenase (*IDH1/2*) (Mardis 2009). Sequence analysis has shown that *IDH* mutations occur in ~ 5% of patients with MDS and 10% of patients with secondary AML. (Kosmider 2010).

*IDH1* is an important metabolic enzyme that catalyzes the conversion of isocitrate to  $\alpha$ -ketoglutarate ( $\alpha$ -KG) in the cytosol, leading to the production of reduced nicotinamide adenine dinucleotide phosphate (NADPH), while *IDH2* is a homologous protein catalyzing this reaction in mitochondria. *IDH1/2* mutations are frequently-found alterations in AML (approximately 5% with *IDH1* and 15% with *IDH2* mutations), gliomas and secondary glioblastomas (Ducray 2009), and have also been detected less commonly in other malignancies. These recurrent mutations are missense alterations affecting arginine 132 (R132) of *IDH1*, and either the analogous arginine residue (R172) or arginine 140 (R140) of the *IDH2* protein (Mardis 2009, Gross 2010, Marcucci 2010, Paschka 2010, Ward 2010).

The identification of neomorphic *IDH1/2* enzyme activity associated with underlying mutations provided a promising therapeutic direction in the treatment of AML and MDS (Abbas 2010, DiNardo 2016, Medeiros 2017). In place of catalyzing the normal process of isocitrate decarboxylation, the altered *IDH* proteins instead facilitate a reduction of  $\alpha$ -KG to 2-hydroxyglutarate (2-HG) (Dang 2009), a metabolite normally present at very low levels. 2-HG has since been shown to directly confer oncogenic activity, likely through interfering with regulation of gene transcription controlled by epigenetic modification of DNA and histones (Xu 2011, Figueroa 2010). These findings have helped encourage the development of *IDH1* and *IDH2* inhibitors, which demonstrated great promise in preclinical evaluation. They are now

---

CONFIDENTIAL

This document is confidential. Do not disclose or use except as authorized.

being actively studied in clinical trials, with very encouraging results, suggestive of effective clinical activity. Rates of remission, partial remission, and stable disease for enasidenib and ivosidenib are remarkable for such patients, including many with relapsed and refractory *IDH*-mutant disease. Enasidenib is now approved for use by the Food and Drug Administration in patients with relapsed/refractory *IDH2*-mutated AML.

The initial promise of *IDH* inhibitors has garnered interest to better understand the most optimal manner by which to incorporate such therapies into conventional paradigms for treatment of *IDH1/2*-mutant myeloid malignancies. Given the increasing employment and success of HSCT in patients with intermediate or high-risk AML (Davies 2008), as well as in those with myelodysplastic syndromes or myeloproliferative neoplasms, the role of novel targeted therapies as maintenance therapy following HSCT is being actively studied to determine their promise in enhancing relapse-free and overall survival. Maintenance following HSCT is routinely used with available inhibitors of the BCR-ABL tyrosine kinase in patients with chronic myeloid leukemia (CML) (Klyuchnikov 2010), or Philadelphia chromosome positive- acute lymphoid leukemia (Kebriaei 2012), even without any prospective trials showing a clear benefit. There is evidence, however, that introducing BCR-ABL inhibitors at the time of detectable minimal residual disease following HSCT can induce long-term remissions in CML (Hess 2005). In addition, anecdotal reports, followed by our own clinical research, suggest substantial promise in using FLT3 inhibitors, such as sorafenib, as maintenance therapy in *FLT3-ITD* mutated AML patients following HSCT (Chen 2014). As an increasing number of targeted and well-tolerated therapies are developed, the paradigm of maintenance therapy after HSCT will likely garner more attention, suggesting a need to conduct well-informed clinical trials to assess efficacy, tolerability, and cost-effectiveness of these therapies.

### **2.3 Ivosidenib**

The investigational drug ivosidenib (AG-120) is a selective, potent inhibitor of the isocitrate dehydrogenase-1 (*IDH1*) mutant protein. Isocitrate dehydrogenase is a critical enzyme in the citric acid cycle catalyzing the oxidative decarboxylation of isocitrate to produce carbon dioxide (CO2) and alpha-ketoglutarate (α-KG). The mutant *IDH* enzymes are not catalytically inactive, but rather possess a novel enzyme activity, catalyzing the reduction of α-KG to the “oncometabolite” 2-hydroxyglutarate (2-HG) (Dang 2009) which has been found to be elevated in patients with several tumor types, including both solid and liquid tumors (Fathi 2012, DiNardo 2013, Janin 2014).

Initial studies sought to identify *IDH1* mutant-selective inhibitors that can suppress 2-HG production in cancer cells. AG-120 is a selective inhibitor of *IDH1* (R132) mutant enzymes with concentrations of drug that achieved half maximal inhibition (IC50) in the range of 2 to 17 nM. Ivosidenib is also a slow binding inhibitor of *IDH1* wild-type (WT) enzymes with an IC50 of 71 to 24 nM following incubation with nicotinamide adenine dinucleotide phosphate (NADP) for either 1 or 16 hours, respectively. Ivosidenib showed no inhibition of isocitrate dehydrogenase-2 (*IDH2*) isoforms at micromolar concentrations.

The results of a series of nonclinical PK studies, including both single dose and multiple dose evaluations, in Sprague-Dawley rats, beagle dogs, and cynomolgus monkeys showed that

---

CONFIDENTIAL

This document is confidential. Do not disclose or use except as authorized.

ivosidenib has an acceptable ADME profile for continued evaluation and development in humans. The toxicity profile of ivosidenib was evaluated *in vitro* in a bacterial reverse mutation, a micronucleus, and a phototoxicity assay and *in vivo* in Sprague-Dawley rats, cynomolgus monkeys, and New Zealand white rabbits, including two 28-day and two 3-month repeat-dose pivotal GLP studies conducted in rats and monkeys, definitive embryo/fetal development studies in rats and rabbits and a micronucleus study in rats. Preliminary clinical data have shown ivosidenib to be generally well-tolerated at the doses evaluated. Substantial reductions in mean plasma 2-HG concentrations have been observed in patients treated with ivosidenib, as well as evidence of clinical activity.

An *in vitro* study of human liver microsomes using chemical inhibitors and recombinant human cytochrome P450 (CYP) enzymes suggested that ivosidenib is mainly metabolized by CYP3A4, with minor contributions from CYP2B6 and CYP2C8. Therefore, coadministration with CYP3A4 inhibitors could have an effect on the pharmacokinetics of ivosidenib.

The AG-120 clinical development program was initiated in March 2014 with 2 Phase 1 first-in-human studies, Study AG120-C-001 in subjects with advanced hematologic malignancies that harbor an *IDH1* mutation and Study AG120-C-002 in subjects with advanced solid tumors, including glioma, that harbor an *IDH1* mutation. Two combination studies in subjects with newly diagnosed AML are also ongoing. Study AG120-221-C-001 is evaluating treatment with AG-120 or AG-221 (an *IDH2* mutant inhibitor) in combination with standard AML induction and consolidation therapy in subjects with AML who are eligible for intensive chemotherapy and Study AG-221-AML-005 is assessing the treatment with AG-120 or AG-221 in combination with azacitidine in subjects with AML not eligible for intensive induction chemotherapy.

Dose escalation has stopped in Studies AG120-C-001 and AG120-C-002. A dose of 500 mg QD has been identified to be used in the expansion arms of both studies to further evaluate the safety and efficacy of AG-120 in subjects with advanced malignancies; 500 mg QD is also the dose being used in the 2 Phase 1/2 combination studies of AG-120 and in the initiated/planned Phase 3 studies.

Preliminary data have shown AG-120 to be well tolerated at total daily doses up to 1200 mg; the maximum tolerated dose (MTD) was not reached in either of the dose escalation studies (DiNardo 2015; DiNardo 2016).

The most commonly reported adverse events (AEs) observed in subjects with cancer demonstrated an acceptable safety profile of ivosidenib. The most common AEs in Study AG120- C-001 were diarrhea (30%), nausea (26%), fatigue (26%), febrile neutropenia (22%), and leukocytosis (22%); in Study AG120-C-002, nausea (28%), fatigue (28%), and diarrhea (23%) were the most common AEs.

## 2.4 Rationale

Given that a substantial proportion of patients with *IDH1/2*-mutant myeloid malignancies are likely candidates for, and will undergo HSCT as a therapeutic modality for their disease, as well as the promise suggested by studies of other novel agents in the post-HSCT setting, it is important to establish the safety and tolerability of these agents in the post-transplant setting as

CONFIDENTIAL

This document is confidential. Do not disclose or use except as authorized.

well as to gain an appreciation of their efficacy in maintaining relapse-free survival in this patient population. The primary goal of this phase I study is to define the recommended phase 2 dose (R2PD) of the mIDH1 inhibitor, ivosidenib (AG-120), as maintenance therapy following HSCT.

## 2.5 Correlative Studies Background

### 2.5.1 2-hydroxyglutarate levels

An intriguing finding in *IDH*-mutant AML is elevated levels of the oncometabolite 2-HG. Initial studies of patient samples revealed greater than 50-fold higher levels of 2-HG, when compared to those from *IDH*-WT patients (Ward 2010). 2-HG levels were then measured in sera and leukemic blasts from a limited number of patients with *IDH*-mutant AML. The *IDH*-mutant samples exhibited elevations of 2-HG above 1,000ng/ml in serum, in contrast to *IDH* wild-type samples (Gross 2010).

We have ongoing efforts to monitor 2-HG levels in *IDH*-mutant patients undergoing traditional chemotherapy for AML. To date, we have noted markedly elevated levels of circulating 2-HG in multiple fluid compartments, including blood, urine, and marrow (Fathi 2012). We found that blood and urine 2-HG levels, serially measured during therapy, directly parallel therapeutic response, and may serve as biomarkers of clinical activity. Assessing levels of a surrogate non-invasive biomarker, such as 2-HG, may allow clinicians to better prognosticate, risk-stratify, and manage patients with AML.

### 2.5.2 Next-generation sequencing (NGS)

*IDH1/2* mutant allelic burden may play an important role in the clinical evolution, diagnostic features, and therapeutic response of *IDH*-mutant AML. The prognostic impact of *IDH* mutations has been evaluated in multiple retrospective studies to date, with largely inconclusive results (Patel 2012, Mardis 2009, Marcucci 2010, Paschka 2010). *IDH* allelic burden has not been extensively studied. Based on data from three *IDH*-mutant patients receiving induction chemotherapy, we found that 2-HG levels correlated with *IDH*-mutational burden during the course of treatment. Through next-generation sequencing (NGS) of serial samples, we found that *IDH1/2* mutational burden (mutant allele as fraction of total *IDH* reads) decreased over time concordantly with serum 2-HG. Based on these preliminary data, it appears that 2-HG levels, along with assessment of *IDH* mutational burden, may parallel the clinical course of *IDH* mutant disease and its response to treatment. We will use next-generation sequencing to assess *IDH1* mutational burden in our participants.

### 2.5.3 Whole Genome Sequencing (WGS)

Whole genome sequencing (WGS) has revealed extensive clonal heterogeneity in AML. The initial (“Founding”) clone contains 500-1000 somatic mutations on average. Subclones frequently emerge, either during the natural history of the disease, or at relapse following therapy. Subclones acquire additional mutations, but retain all mutations present in ancestral clones (Welch 2012, Ding 2012, Jan 2012, Walter 2012).

---

CONFIDENTIAL

This document is confidential. Do not disclose or use except as authorized.

The sequence of mutations acquired by preleukemic clones, as they transform, is informative since it can distinguish initiating mutations from those which are cooperating alterations. *IDH1/2* mutations are often present in the founding clone (and, therefore, are retained in subclones) (Ding 2012, Walter 2012). Little is known about the relative sensitivity of *IDH*-mutant vs. wildtype clones to conventional cytotoxic chemotherapy or the impact of targeted therapy on the clonal architecture of *IDH* mutant AML.

Indeed, the landscape of leukemic subpopulations is dynamic and evolves over time, either due to progression of disease, or in response to selective pressure from treatment (Jan 2012). The clonal architecture, comprised of subclones with distinct mutational profiles, can vary during the course of treatment, and a small subclone present at diagnosis may develop into the dominant clone at relapse. Through whole genome sequencing, we will more fully characterize the clonal architecture and evolution of relapse of *IDH*-mutant AML.

#### 2.5.4 Minimal Residual Disease (MRD)

In the phase 1 study of ivosidenib in myeloid malignancies, a proportion of relapsed and refractory patients were found to have cleared the mutant (mIDH1) allelic burden (Stone 2017). Indeed, MRD-negativity was observed in 7 of 25 (28%) R/R AML patients who achieved CR, and those with MRD-negative CR had improved CR duration and overall survival, albeit the dataset was small. MRD-negativity by mIDH1 status was also observed in 5 of 9 patients with untreated AML who achieved CR or CRh. We therefore seek to assess MRD clearance by measuring mIDH1 allelic burden at time points throughout the study.

---

CONFIDENTIAL

This document is confidential. Do not disclose or use except as authorized.

### 3. PARTICIPANT SELECTION

#### 3.1 Eligibility Criteria

Participants must meet the following criteria to be eligible for enrollment on this study.

- 3.1.1 Pathologically confirmed diagnosis of *IDH1(R132)*-mutant acute myeloid leukemia (AML), myelodysplastic syndrome (MDS) or chronic myelomonocytic leukemia (CMML). *IDH1* mutations could have been detected by any mutational technique at any prior point including at diagnosis or remission.
- 3.1.2 Age  $\geq 18$
- 3.1.3 Will undergo allogeneic hematopoietic stem cell transplantation (HSCT) for their malignancy. Conditioning may be either conventional myeloablative (MAC) or reduced intensity conditioning (RIC).
- 3.1.4 HSCT Donor will be one of the following:
  - 5/6 or 6/6 (HLA-A, B, DR) matched related donor
  - 7/8 or 8/8 (HLA-A, B, DR, C) matched unrelated donor. Matching in the unrelated setting must be at the allele level.
  - Haploidentical related donor, defined as  $\geq 3/6$  (HLA-A, B, DR) matched
  - $\geq 4/6$  (HLA-A, B, DR) umbilical cord blood (UCB). Matching in the UCB setting is at the antigen level. Recipients may receive either one or two UCB units. In the case of 2 UCB units, both units must have been at least 4/6 matched with the recipient.
- 3.1.5 ECOG performance status  $\leq 2$
- 3.1.6 Participants must have normal organ and marrow function as defined below:
  - Absolute neutrophil count  $\geq 1000/\mu\text{L}$  without growth factor support (e.g. GCSF) in the previous 7 days. This criterion does not apply to patients with myelodysplastic syndromes, myeloproliferative neoplasms in leukemic phase, or CMML, who will not necessarily be expected to achieve marrow recovery prior to HSCT.
  - Platelet count  $\geq 50,000/\mu\text{L}$  without transfusional support in the previous 7 days. This criterion does not apply to patients with myelodysplastic syndromes, myeloproliferative neoplasms in leukemic phase, or CMML, who will not necessarily be expected to achieve marrow recovery prior to HSCT.
  - AST (SGOT), ALT (SGPT) and Alkaline phosphatase  $< 3x$  institutional upper limit of normal (ULN)
  - Direct bilirubin  $< 2.0 \text{ mg/dL}$
  - Calculated creatinine clearance  $\geq 40 \text{ mL/min}$  (Cockcroft-Gault formula)

---

CONFIDENTIAL

This document is confidential. Do not disclose or use except as authorized.

- 3.1.7 LVEF must be equal to or greater than 40%, as measured by MUGA scan or echocardiogram
- 3.1.8 Female patients of childbearing potential must have a negative pregnancy test
- 3.1.9 The effects of ivosidenib on the developing human fetus are unknown. For this reason female participants of child-bearing potential and male participants must agree to use adequate contraception (hormonal or barrier method of birth control; abstinence) during the entire study treatment period and through 90 days after the last dose of treatment
- 3.1.10 Ability to understand and the willingness to sign a written informed consent document.

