## 5.5 General Concomitant Medication and Supportive Care Guidelines

Ivosidenib (AG-120) is a substrate and a potential inducer of CYP2B6 and CYP3A4. Co-administration of AG120 with drugs primarily metabolized by CYP2B6 or 3A4 may result in decreased plasma concentrations of the co-administered drug. Therefore, concurrent use of CYP3A4 substrates should be avoided when possible, but when medically necessary, appropriate dose adjustments of the co-administered drug may be necessary. Examples of CYP3A4 substrates with narrow therapeutic index include cyclosporine, everolimus, sirolimus, and tacrolimus. Careful monitoring of drug levels of immunosuppressant agents is required. Careful consideration should be given to whether participants require the use of azoles and quinolones. An appendix E outlines list of strong CYP3A4 inhibitors, CYP3A4 substrates, and inducers.

Concomitant administration with strong CYP3A4 inhibitors is predicted to increase ivosidenib steady-state C max by up to 52% and AUC by up to 90% which may increase the risk of QTc interval prolongation. Treatment with strong CYP3A4 inhibitors is allowed on this study when they are medically necessary and cannot be avoided or substituted with another medication. However dose adjustment will be necessary with strong CYP3A4 inhibitors (listed in Appendix E) are used concurrently. This will be outlined in section 6.4. Additionally, the investigators must monitor for any changes in toxicity or QT interval, as outlined in section 6.5. Monitoring of subjects receiving study treatment with the combination of these drugs is essential. Providers and investigators should evaluate ECG and electrolytes (including potassium, magnesium, and calcium) at least weekly for the first cycle of therapy. Vigilance is particularly important in subjects presenting with nausea, vomiting, or diarrhea.

Intrathecal chemotherapy for the purposes of prophylaxis is allowed. Intrathecal chemotherapy for the purpose of treating active leukemic disease is not allowed.

If treatment pauses are necessary, per guidance below, due to adverse events on study, if and when ivosidenib is held in the midst of a cycle, the cycle day will not change, and once the drug is resumed it will be either on the day that that cycle has progressed to, or if the pause is beyond 28 days of that cycle, the resumption will be called the day 1 of the subsequent cycle.

---

CONFIDENTIAL

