### 6.4 Concurrent Use of CYP3A4 Inhibitors, CYP3A Inducers, and CYP3A Substrates

Dose adjustment of ivosidenib will be necessary when strong CYP3A4 inhibitors (listed in Appendix E) are initiated or used concurrently, given that concomitant administration with strong CYP3A4 inhibitors is predicted to increase ivosidenib steady-state C max by up to 52% and AUC by up to 90%. For patients at an ivosidenib dose of 500mg daily, concomitant use of strong CYP3A4 inhibitors, the ivosidenib dose will be reduced to 250mg daily, with close monitoring for any toxicity or QT interval prolongation.

The concomitant use of CYP3A inducers (listed in Appendix E) should be avoided. As for concomitant use of CYP3A substrates, this should be avoided when possible, but when this is medically necessary, very close monitoring for toxicity is needed. As an example, tacrolimus and sirolimus are both common immunosuppressive medications, and CYP3A substrates, that post-transplant participants may be taking. Both of these agents will be monitored closely in terms of trough levels, with levels will be doses closely followed and adjusted.

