### 7.1 Potential Risks and Adverse Drug Reactions (ADRs) for Ivosidenib

Please refer to the current Investigator's Brochure (IB) for ivosidenib which includes any additional updated safety data and drug-drug interaction information.

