## Appendix E

### Strong CYP3A4 inhibitors – this will trigger dose reduction to 250 mg daily

Drug Type	Generic
HIV Protease Inhibitors	Indinavir Nelfinavir Lopinavir Ritonavir Saquinavir
Food	Grapefruit juice
Others – note common antifungals	Boceprevir Telaprevir Clarithromycin Telithromycin Conivaptan Itraconazole Ketoconazole Posaconazole Voriconazole Nefazodone

**CYP3A substrates (use caution and monitor) – examples include:** alfentanil, avanafil, buspirone, conivaptan, darifenacin, darunavir, ebastine, everolimus, ibrutinib, lomitapide, lovastatin, midazolam, naloxegol, nisoldipine, saquinavir, simvastatin, sirolimus, tacrolimus, tipranavir, triazolam, vardenafil, budesonide, dasatanib, dronedarone, eletriptan, eplerenone, felodipine, indinavir, lurasidone, maraviroc, quetiapine, sildenafil, ticagrelor, tolvaptan.

**Note: Tacrolimus and sirolimus are both listed here and are common immunosuppressive medications that participants will be taking. Both of these agents will be monitored closely in terms of trough levels with doses adjusted.**

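### Section 3.1.9 accepts hormonal contraception alone, although section 5.5 warns that ivosidenib may induce CYP3A4 and so might weaken it

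*Combined protocol and SAP*

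**What the plan says.** Section 3.1.9 gives uncertainty about fetal effects as its reason for requiring contraception. Women of childbearing potential and men "must agree to use adequate contraception (hormonal or barrier method of birth control; abstinence) during the entire study treatment period", and for a further 90 days after the last dose. The hormonal option is not limited by product or route, and no second method is required.

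Section 5.5 states: "Ivosidenib (AG-120) is a substrate and a potential inducer of CYP2B6 and CYP3A4". It continues: "Co-administration of AG120 with drugs primarily metabolized by CYP2B6 or 3A4 may result in decreased plasma concentrations of the co-administered drug". Its general advice is that "concurrent use of CYP3A4 substrates should be avoided when possible"; where a substrate is medically needed, "appropriate dose adjustments of the co-administered drug may be necessary".

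Section 6.4 repeats the advice to avoid CYP3A substrates and adds that "when this is medically necessary, very close monitoring for toxicity is needed". Appendix E gives examples of substrates, none of them a hormonal contraceptive, and says of tacrolimus and sirolimus: "Both of these agents will be monitored closely in terms of trough levels with doses adjusted".

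Section 7.1 sends investigators to the Investigator's Brochure, which "includes any additional updated safety data and drug-drug interaction information". Footnote 6 of the study calendar requires a pregnancy test in the week before dosing at each cycle for women of childbearing potential. Section 7.7 requires a pregnancy to be reported within 24 hours of the site learning of it.

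**The concern.** The eligibility rule and the interaction warning do not refer to each other. Site staff applying 3.1.9 would accept a woman whose only contraception is hormonal, because the criterion names that method. The warning in 5.5 implies that the same method could lose exposure once ivosidenib starts, if it is cleared mainly by CYP3A4 or CYP2B6.

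What is at stake is the safety of the participant and of a possible fetus. The criterion exists to prevent conception during exposure to a drug whose fetal effects are not known. Followed to the letter, it could leave a woman relying on a method that the study drug weakens.

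**Working it through.** The plan states no figure on this point to reproduce. The check sets the sections side by side and then sizes the group concerned.

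**Step 1: does 3.1.9 allow a hormonal method alone?** Yes. The list is joined by *or*, and nothing else in the available text adds a second method.

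**Step 2: does the plan warn of lower substrate levels?** Yes. Section 5.5 says so for drugs cleared mainly by CYP2B6 or CYP3A4, and describes the induction as potential.

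**Step 3: are hormonal contraceptives such drugs?** The documents do not say. The assumption here is that many systemic contraceptive steroids are CYP3A4 substrates. This is general pharmacology, varies by product and route, and has to be checked against the Brochure. Where it fails, as it may for a locally acting method, the point does not apply.

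**Step 4: would another provision close the gap?**

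| Provision | What it does | Does it prevent contraceptive failure? |
|---|---|---|
| 5.5, avoid substrates or adjust their dose | General advice; contraceptives not named | Points that way, but requires no back-up |
| 6.4, monitoring | Looks for toxicity | No; reduced effect is not toxicity |
| Appendix E, trough levels | Covers tacrolimus and sirolimus | No |
| Study calendar, pregnancy tests | Detects pregnancy | No |
| 7.7, 24-hour reporting | Reports a known pregnancy | No |
| 7.1, Brochure | Points to interaction information | Unknown; the Brochure is not part of the documents |

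**Step 5: how many participants, and for how long?** Evaluable patients, from sections 5.1 and 13:

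- Minimum, with at least 2 of 3 DLTs at both doses: 3 + 3 = 6.
- No de-escalation: 6 + 10 = 16.
- Maximum: 6 + 6 + 10 = 22.

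The range of 6 to 22 agrees with the Sample Size paragraph. The share of participants who are women of childbearing potential relying on a systemic hormonal method alone is not in the documents. An assumed range of 0 to 10% gives, as share × number of patients:

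| Assumed share | of 6 | of 16 | of 22 |
|---|---|---|---|
| 0% | 0 | 0 | 0 |
| 5% | 0.3 | 0.8 | 1.1 |
| 10% | 0.6 | 1.6 | 2.2 |

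Replaced participants would add slightly to these counts. Men are not affected, since the interaction acts in the person taking ivosidenib.

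Planned dosing lasts 12 × 28 = 336 days. With the 90 days that follow, the existing contraception window is 336 + 90 = 426 days. The concern applies mainly to the 336 days; the documents do not show that induction continues through the later 90.

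**The case against.** The strongest objection is that the decisive link, that contraceptive steroids are CYP3A4 substrates, appears nowhere in the documents. Without it 3.1.9 and 5.5 do not conflict. That is true, and it is why the conclusion is conditional and the Brochure comes first. Even so, the plan warns of induction and does not say whether the contraception it accepts is affected.

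A second objection is that, if the link is real, the plan already deals with it. Sections 5.5 and 6.4 say to avoid substrates where possible, 3.1.9 lists non-hormonal options, and Appendix E gives only examples, so an unlisted drug is not exempt. This has some force: an investigator reading the whole protocol could reach the right answer. But the advice is general and does not mention contraceptives, while 3.1.9 is specific and permits the method by name. Site staff checking eligibility would reasonably follow the specific rule.

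Third, contraception advice may sit in material not available here: the consent pages, some text within or next to 5.5, and the text between 6.5 and 6.7. The absence of a back-up rule is therefore established only for the available text. Advice in those places would reduce the practical risk but would leave the wording of 3.1.9 as it is.

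Finally, the induction is only potential, a permitted strong CYP3A4 inhibitor such as an azole could offset it, and the number of women affected may be zero. All of this stands. It limits the size of the problem, but not every participant will be taking an azole.

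**Conclusion.** The concern holds. The available text accepts hormonal contraception on its own and also warns that the study drug may lower the levels of CYP3A4 and CYP2B6 substrates, with nothing to reconcile the two. The conclusion that contraception may be weakened depends on the pharmacology assumption and is worded accordingly; confidence is moderate.

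The group is small: between 0 and about 2 women even at the maximum sample size, on an assumed share with no source in the documents. The RP2D, the DLT rules and the sample size do not change. The amendment should be made because the possible harm is serious, pregnancy testing and reporting limit undetected exposure without preventing conception, and the correction is cheap.

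**What to change.** Check the Investigator's Brochure for the interaction with hormonal contraceptives. Unless it rules the interaction out, make two changes:

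- **Section 3.1.9:** require female participants of childbearing potential who use systemic hormonal contraception to add a barrier method during ivosidenib treatment, or to use an effective non-hormonal method or abstinence instead. As a precaution, and to match the existing window, apply this through the 90 days after the last dose.
- **Appendix E:** add hormonal contraceptives to the CYP3A substrate note, with a warning that they may be less effective during ivosidenib treatment.

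The cost is one sentence and one line of text, plus a small added burden for women using hormonal methods. The change need not exclude anyone.
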